Attending neurosurgeon decides that frontal EVD indicated for patient treatment with planned CSF drainage for 72 hours or more	Anticoagulated prior to admission and not fully reversed with Coumadin (warfarin), Effient, Plavix, therapeutic heparin infusion, therapeutic subcutaneous Lovenox, therapeutic subcutaneous Arixtra, or other therapeutic anticoagulant or antiplatelet agent (ASA not included)
Glasgow Coma Score of 5 or higher within 12 hours of EVD insertion	Best Glasgow Coma Scale of 4 or less within 12 hours of EVD insertion
	Hunt and Hess subarachnoid hemorrhage grade of 5
	Age 86 or greater
	Plan for placement of EVD through non-frontal burr hole approach

Secondary Outcome Measures

1. Catheter replacement: defined by replacement of the ipsilateral EVD due to permanent occlusion, or placement of a contralateral EVD in the setting of a non-functioning ipsilateral catheter. Catheters placed contralaterally in the setting of a functioning ipsilateral catheter will not be considered replacements.
2. Temporary occlusion: defined by non-functioning (non-patent) catheter requiring neurosurgeon flushing or manipulation in order to restore patency. By definition, such maneuvers must restore patency of the EVD such that it is functioning normally afterwards. Multiple temporary occlusions may be possible.
3. Procedure-related hemorrhage: Presence of new catheter-related intraparenchymal hemorrhage, subdural hematoma, or intraventricular hemorrhage on CT scan after placement.
4. Symptomatic hemorrhage: Presence of new neurologic deficits as a result of EVD-related hemorrhage, or resulting in need for further procedures due to new EVD-related hemorrhage (craniotomy for hematoma evacuation, ICP monitoring, etc).
5. Administration of intraventricular tPA (Tissue Plasminogen Activator) regardless if catheter patency is restored.

Protocol

Once EVD is deemed indicated by the attending neurosurgeon, the patient becomes a candidate for enrollment. At this point, research staff will determine candidacy by reviewing inclusion and exclusion criteria. Patients that meet inclusion criteria, in the absence of exclusion criteria, will be consented and randomized by enrolling the patient in RedCap. Patients who meet inclusion criteria and have no exclusion criteria but cannot be consented before treatment will undergo placement of an EVD, with catheter size based on surgeon preference, and will be enrolled in an ongoing prospective database.

Procedural technique

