All EVD will be placed by neurological surgeons in either the major operating suite or in an ICU setting using a previously published protocol¹². This protocol includes using a burr hole entry point 1 cm anterior to the coronal suture in the mid-pupillary line, prep and sterile drape, pre-procedural antibiotic administration, and tunneling the catheter to an exit site at least 5 cm from the incision. Following EVD insertion, physicians will document procedural factors on the procedural data sheet (Appendix A)

Flushing technique

No formal published protocols exist for catheter irrigation. In general, physicians are instructed to first attempt distal irrigation of the drainage chamber using sterile techniques (rarely effective), followed by gentle aspiration of the proximal system and catheter if distal flushing is not effective. If these do not restore patency, a small volume of sterile saline, 3 ml or less, is flushed proximally into the catheter. Patency is checked by lowering the EVD drainage system and evaluating for spontaneous flow through the EVD. Each irrigation will be recorded on the daily record sheet (Appendix B).

Treatment Arms

Enrolled patients will be randomized to one of two catheters in a 1:1 randomization scheme. These include the antibiotic-impregnated 'large' catheter (outer diameter 3.4 mm, inner diameter 1.9 mm) and an antibiotic-impregnated 'small' catheter (outer diameter 3 mm, inner diameter 1.5 mm). After placement of the EVD catheter, all clinical and radiographic follow-up will be the same for both treatment arms.

Data collection

Data will be collected prospectively by the research team. Trial data will be reported via RedCap. Collected data will include a number of factors, such as: age, gender and underlying diagnosis; procedural data including faculty versus resident physician as primary proceduralist, number of passes, side of placement; radiographic data including ventricular size (based upon Evan's ratio: maximum bifrontal ventricular distance divided by maximal intracranial biparietal distance), pre-procedural midline shift, presence of intraventricular hemorrhage, catheter location, and presence of catheter-related hemorrhage; and clinical data including symptomatic hemorrhage, number and type of catheter irrigations, catheter

occlusion and replacement, number of catheter days, catheter endpoint, cerebrospinal fluid analysis and incidence of catheter-related infection (Appendices).

Imaging Review

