A blinded physician at each treatment center will review brain imaging to document all radiographic data into RedCap, including: Evan's ratio, midline shift, presence of intraventricular hemorrhage, catheter location, and presence of catheter-related hemorrhage. At time of site activation for each center, the radiographic reviewer will undergo a training session via conference call, performed by the study PI (KF), which will ensure consistent interpretation of imaging across centers. The primary center may ask for select image series to be uploaded into RedCap for review by the PI.

Study Endpoint

Patients will have met the study endpoint when the EVD is intentionally removed by the supervising physician, in any of the following scenarios: 1) The EVD is removed due to resolution of hydrocephalus; 2) The EVD is removed because it is non-functional but not replaced; 3) The EVD is removed and is replaced with a shunt. Once the endpoint has been reached, no further data collection will occur for that study subject.

Adverse Events

Adverse events will be recorded. Adverse events include: symptomatic intracranial intraparenchymal or subdural hemorrhage (with new neurologic deficit or need for surgery), symptomatic intraventricular hemorrhage (defined as new neurologic deficit, need for surgery, or catheter occlusion within 2 hours of placement requiring contralateral EVD placement), meningitis (confirmed by positive CSF cultures and initiation of antibiotic therapy), catheter in extraventricular position on placement, and catheter malposition after confirmation of correct positioning requiring replacement (ie. catheter is unintentionally pulled out by nurse, patient, or due to loose sutures).

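### All data collection stops when the EVD is removed, so meningitis or symptomatic haemorrhage that first appears afterwards goes unrecorded, although the protocol undertakes to record adverse events

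*Protocol*

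**What the plan says.** The Study Endpoint section of the protocol sets the trigger: "Patients will have met the study endpoint when the EVD is intentionally removed by the supervising physician, in any of the following scenarios". The first scenario is resolved hydrocephalus. The other two read: "2) The EVD is removed because it is non-functional but not replaced; 3) The EVD is removed and is replaced with a shunt". The section closes with the rule at issue: "Once the endpoint has been reached, no further data collection will occur for that study subject". It gives no period after removal and no exception.

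The Adverse Events section follows directly and undertakes to record adverse events. Its list includes symptomatic haemorrhage and "meningitis (confirmed by positive CSF cultures and initiation of antibiotic therapy"). The Data collection section includes "cerebrospinal fluid analysis and incidence of catheter-related infection" among the items to be gathered. Under Secondary Outcome Measures, symptomatic haemorrhage is the fourth outcome. Catheter replacement is the first, defined as "replacement of the ipsilateral EVD due to permanent occlusion, or placement of a contralateral EVD in the setting of a non-functioning ipsilateral catheter". None of these entries carries a time limit.

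**The concern.** Ending follow-up for the primary outcome at removal is sound, because a catheter that is out can no longer occlude. The rule goes further and ends collection of everything at the same moment. Some of the harms that the protocol undertakes to record can first show themselves after the drain is out.

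This is a stated instruction, not a detail left for the analysis plan. Staff who follow it will not have the data, and no later analysis can restore them. The harm side matters here because the two catheters differ in outer diameter (3.4 mm against 3 mm), and the Background itself raises haemorrhage risk in relation to catheter bore. A trial that finds fewer occlusions with one size would want a complete account of infection and bleeding alongside that result.

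**Working it through.** The protocol states no figure on this point, so the check sets the sections side by side.

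**Step 1: what stops collection.** The stop applies to intentional removal in the three listed scenarios. A failed EVD that is replaced at the time is not among them, so collection continues and the replacement is recorded. An accidental pull-out is not intentional removal and does not trigger the stop either. No section provides for follow-up after the stop. Of the two appendix forms, one covers insertion and the other is a daily sheet built around drain height, clamping and flushing.

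**Step 2: which outcomes and events can fall after the stop.**

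| Outcome or event | Can it first appear after removal? | Recorded under the rule? |
|---|---|---|
| Permanent occlusion (primary outcome) | No, settled by the time of removal | Yes |
| Extraventricular position on placement | No | Yes |
| Malposition of a correctly placed catheter | No | Yes |
| Haemorrhage on CT after placement | Normally seen while the drain is in | Normally yes |
| Symptomatic haemorrhage | Yes, if the deficit or need for surgery emerges later | Not if later |
| Meningitis | Yes, if onset follows removal | Not if later |

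The last two rows are the gap. Both meet the protocol's own definitions, which set no time limit, and both fall after the cut-off. This holds for all three removal scenarios and for both arms.

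**Step 3: re-insertion after a failed drain.** The second scenario is "The EVD is removed because it is non-functional but not replaced". Staff can judge this only at removal, and no period is given over which the drain must remain unreplaced. Suppose the drain had permanently occluded and a new ipsilateral EVD is placed some days later for the same reason. That re-insertion could meet the first secondary outcome, which has no time limit, but collection has already ended.

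**Step 4: size.** With 120 patients planned, the expected number of patients with an unrecorded event is 120 × r, where r is the proportion with a first meningitis or symptomatic haemorrhage after removal. Each percentage point of r corresponds to 120 × 0.01 = 1.2 patients. The protocol gives neither r nor the rates needed to build it, so the number cannot be derived. The same is true of late re-insertion: the document does not say how often a failed drain is removed without replacement, or how often such a patient later needs another.

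**The case against.** The strongest reply is that the loss is narrow. Planned drainage is at least 72 hours, so bleeding caused by placement should normally be seen before removal. Several listed adverse events can occur only with the catheter in place. Meningitis is neither a primary nor a secondary outcome. A culture taken before removal is a specimen from within the collection period, and entering its pending result need not count as further collection. All of this stands. What remains is meningitis with onset after removal and haemorrhage that becomes symptomatic after removal. Nothing in the protocol allows these to be recorded.

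On replacement, the reply is that a new EVD placed after a deliberate decision not to replace may not be a replacement at all. The contralateral limb of the definition reads most naturally as referring to a failed catheter still in place. This also has force: the late re-insertion counts only on a broad reading, and only in a small subgroup. The definition does not exclude it, however, which is why a time limit is needed.

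A reader might infer three stronger things, and the documents support none of them:

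- **That the comparison is biased.** The second scenario is triggered by catheter failure, which the trial expects to differ by arm. That alone does not distort the comparison. If the share of failures missed is equal in both arms, replacements are under-counted in proportion and the risk ratio is unchanged. Nothing in the protocol suggests unequal shares.
- **That the rule contradicts the sentence "After placement of the EVD catheter, all clinical and radiographic follow-up will be the same for both treatment arms".** It does not. One stop rule applies to both arms, and follow-up that varies with time in place is inherent in a trial of catheter survival.
- **That replacements in general go unrecorded.** They do not, because immediate replacement is outside the three stopping scenarios. Any figure for missed replacements would rest on assumed shares. It would also apply them to occlusions that the Background describes as requiring replacement.

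**Conclusion.** The point holds for safety capture. The Study Endpoint rule and the undertaking to record adverse events and infection cannot both be followed for an event that first appears after removal. Meningitis and symptomatic haemorrhage are the events affected, in both arms and for every listed removal reason. The missing time limit on the scenario without replacement is a smaller, related gap.

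The conclusion assumes only that staff follow the rule as written. Its numerical size cannot be computed from the protocol. The primary outcome is unaffected, as are events arising while the drain is in place, and no bias between arms is shown. The change is worth making because it is cheap and because data never collected cannot be recovered, not because the main result is in danger.

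**What to change.** Separate two stopping points in the Study Endpoint section:

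1. Ascertainment of the primary outcome ends when the randomised catheter is removed.
2. Collection of infection, symptomatic haemorrhage and any further EVD continues by chart review for a stated window after removal. Discharge is one possible end. The length is for the investigators to choose, but it should be the same in both arms and for every removal reason.

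In the definition of catheter replacement, state within what time a new EVD counts as a replacement, and align the second removal scenario with it.

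The cost is a few sentences and one late chart review per patient. No visits or procedures are added and the sample size does not change.

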APPENDIX A:

EVD Insertion Procedure Datasheet

Subject No: _____

Date: _____

Side (Circle one): Right Left

Year of Physician Performing Procedure (Circle one):

PGY1 PGY2 PGY3 PGY4 PGY5 PGY6 PGY7 Faculty

Number of Passes Required (Circle one):

1 2 3 4 5 6 7 8 9 10 11 or more

Degree of Confidence Ventricular Catheter in Ipsilateral Lateral Ventricle, from 1-5 (Circle one):

1 2 3 4 5
(Poor Confidence) (Moderate Confidence) (Highly Confident)

APPENDIX B:

STUDY SUBJECT DAILY RECORD SHEET

Subject No: _____

Date: _____

Side (Circle one): R L

At time 00:00, EVD is (Circle one): Clamped Open to Drain

At time 00:00, Height of EVD (cm of water): _____

RECORD ANY EVD HEIGHT OR CLAMPING ORDER CHANGES:

Height Change #1: Changed to: _____ cm water Time:

Height Change #2: Changed to: _____ cm water Time:

Height Change #3: Changed to: _____ cm water Time:

Clamping/Unclamping #1: Clamped Unclamped Time:

Clamping/Unclamping #2: Clamped Unclamped Time:

Clamping/Unclamping #3: Clamped Unclamped Time:

RECORD ANY EVD FLUSHING EVENTS:

1. Time:	 Distal system flushed only	 Proximal system aspirated only
	 Proximal system flushed - number of times: _____	
	RESULT:  EVD functioning  EVD occluded	
2. Time:	 Distal system flushed only	 Proximal system aspirated only
	 Proximal system flushed - number of times: _____	
	RESULT:  EVD functioning  EVD occluded	
3. Time:	 Distal system flushed only	 Proximal system aspirated only
	 Proximal system flushed - number of times: _____	
	RESULT:  EVD functioning  EVD occluded	
4. Time:	 Distal system flushed only	 Proximal system aspirated only
	 Proximal system flushed - number of times: _____	
	RESULT:  EVD functioning  EVD occluded	
5. Time:	 Distal system flushed only	 Proximal system aspirated only
	 Proximal system flushed - number of times: _____	
	RESULT:  EVD functioning  EVD occluded	

6. Time:	 Distal system flushed only	 Proximal system aspirated only
	 Proximal system flushed - number of times: _____	
	RESULT:  EVD functioning  EVD occluded	
7. Time:	 Distal system flushed only	 Proximal system aspirated only
	 Proximal system flushed - number of times: _____	
	RESULT:  EVD functioning  EVD occluded	
8. Time:	 Distal system flushed only	 Proximal system aspirated only
	 Proximal system flushed - number of times: _____	
	RESULT:  EVD functioning  EVD occluded	
9. Time:	 Distal system flushed only	 Proximal system aspirated only
	 Proximal system flushed - number of times: _____	
	RESULT:  EVD functioning  EVD occluded	
10. Time:	 Distal system flushed only	 Proximal system aspirated only
	 Proximal system flushed - number of times: _____	
	RESULT:  EVD functioning  EVD occluded	
11. Time:	 Distal system flushed only	 Proximal system aspirated only
	 Proximal system flushed - number of times: _____	
	RESULT:  EVD functioning  EVD occluded	
12. Time:	 Distal system flushed only	 Proximal system aspirated only
	 Proximal system flushed - number of times: _____	
	RESULT:  EVD functioning  EVD occluded	
13. Time:	 Distal system flushed only	 Proximal system aspirated only
	 Proximal system flushed - number of times: _____	
	RESULT:  EVD functioning  EVD occluded	
14. Time:	 Distal system flushed only	 Proximal system aspirated only
	 Proximal system flushed - number of times: _____	
	RESULT:  EVD functioning  EVD occluded	
15. Time:	 Distal system flushed only	 Proximal system aspirated only
	 Proximal system flushed - number of times: _____	
	RESULT:  EVD functioning  EVD occluded
